5.3.3 Sensitivity Analyses

No sensitivity analysis is planned.

5.3.4 Supplementary Analyses

No supplementary analysis is planned.

5.4 Secondary Endpoint(s) Analysis

5.4.1 Key/Confirmatory Secondary Endpoint(s)

Refer to main SAP v2.0, dated 25 JAN 2023.

5.4.1.1 Definition of Endpoint(s)

Refer to main SAP v2.0, dated 25 JAN 2023.

5.4.1.2 Main Analytical Approach

DOR (duration of response), DCR (disease control rate), PFS (progression free survival) and OS (overall survival) will be presented, following same analyses as those at primary completion.

AEs will be presented following same analyses as those at primary completion.

5.4.1.3 Sensitivity Analyses

No sensitivity analysis is planned.

5.4.1.4 Supplementary Analyses

No supplementary analysis is planned.

5.4.2 Supportive Secondary Endpoint(s)

Not applicable.

5.5 Tertiary/Exploratory Endpoint(s) Analysis

5.5.1 Tertiary Endpoint(s)

Tertiary or exploratory efficacy endpoints will not be presented.

Version 3.0 Page: 6 of 9

5.5.1.1 Definition of Endpoint(s)

Not applicable

5.5.1.2 Main Analytical Approach

Not applicable

5.6 (Other) Safety Analyses

5.6.1 Extent of Exposure

Analyses of treatment duration, dose modifications will be conducted as described in main SAP v2.0, dated 25 JAN 2023.

5.6.2 Adverse Events

AEs are described in Section 5.4.

Deaths:

Analyses of deaths will be conducted as described in main SAP v2.0, dated 25 JAN 2023.

Immune-Mediated Adverse Events (IMAE) and Immune-modulating medication:

Analyses of IMAE and Immune-modulating concomitant medications will be conducted as described in main SAP v2.0, dated 25 JAN 2023.

5.6.3 Additional Safety Assessments

Clinical laboratory data:

Clinical laboratory will be presented per main SAP v2.0, dated 25 JAN 2023

ECG:

12-lead ECG will not be presented.

Vital signs and ECOG PS:

Analyses of vital signs, ECOG PS will be conducted as described in main SAP v2.0, dated 25 JAN 2023.

Pregnancies:

Pregnancy tests will not be presented.

5.7 Other Analyses

5.7.1 Other Variables and/or Parameters

Following analyses will be created per cohort to support efficacy analyses:

Version 3.0 Page: 7 of 9

- Time to follow-up: the duration of follow-up defined as time from start of study-drug intake to last contact or death at the database cut-off date. Time will be summarized using descriptive statistics (number of observations, mean, standard deviation, minimum, median and maximum).

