Nivolumab is approved for treatment of recurrent or metastatic HNSCC that are platinumresistant based on data showing improved survival compared to treatment with single-agent chemotherapy (hazard ratio [HR] 0.70; 97.73% confidence interval [CI], 0.51 to 0.96; P =0.01) (Ferris et al. 2016). The median OS for the nivolumab group was 7.5 months (95% CI, 5.5 to 9.1) and ORR was 13%. The activity of nivolumab as single agent and early clinical data from studies of PD-1 inhibitor in combination with an anti-angiogenic MKI suggest exploring the potential for combing nivolumab with regorafenib to improve clinical results for patients with advanced HNSCC.

Little is known regarding the effectiveness of ICI rechallenge after disease progression following initial ICI treatments in HNSCC and other solid tumors. Many previous trials involving ICI excluded patients who have received prior ICI. As ICIs have received expanded approval for different tumor indications including broader application for initial treatment in HNSCC, an unmet need exists to assess whether a rechallenge with an ICI in combination with another agent may overcome resistance to initial ICI treatment and improve response. There is early indication that a rechallenge with ICI in combination with a MKI may allow some solid tumors that have progressed on prior ICI to respond. In the REGONIVO study, 3 of 7 GC patients who were refractory to previous PD-1-targeted therapy achieved response with regorafenib plus nivolumab. The ORR was 42.8% (3 out of 7) for GC patients who progressed on prior ICI and 44% (11 out of 25) among all GC patients (Fukuoka, Hara et al. 2020). Among the 7 responders out of 21 patients with advanced NSCLC, 2 participants who progressed on prior ICI therapy achieved responses (1 complete response [CR] and 1 partial response [PR]) upon treatment with lenvatinib in combination with pembrolizumab (Taylor et al. 2020). These results are encouraging and warrant further study to address whether the combination regorafenib with nivolumab can elicit anti-tumor response in patients with HNSCC who have progressed on prior ICI therapy.

Esophageal Squamous Cell Carcinoma

Esophageal cancer, the sixth most common cause of cancer deaths worldwide, has an incidence of 570,000 cases annually (Bray et al. 2018, WHO-IARC 2018). The most common subtype globally is ESCC which accounts for 88% of all esophageal cancer (Abnet et al.

CONFIDENTIAL

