27 JAN 2021

2018). ESCC occurs most commonly in Asia, Eastern Africa, and South America. The 5-year survival rate is 5% for patients diagnosed with metastatic disease (NIH-SEER 2020). In a randomized control Phase 3 trial (ATTRACTION-3), nivolumab improved survival versus chemotherapy (paclitaxel or docetaxel) (median OS 10.9 months vs 8.4 months, HR 0.77, 95% CI 0.62-0.96; p=0.019) irrespective of tumor PD-L1 expression in subjects with unresectable advanced, recurrent or metastatic ESCC previously treated with fluoropyrimidine- and platinum-based chemotherapy (Kato et al. 2019). Treatment with nivolumab was associated with an ORR of 19% and a favorable safety profile. Despite this progress, a high unmet need remains to explore a combinatorial approach to enhance the anti-tumor effects of PD-1 inhibition in patients with ESCC.

Pancreatic Duct Adenocarcinoma

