4.1.4 Long-Term FU

All surviving participants will enter the long-term FU period after discontinuing from the active FU period except for participants who explicitly withdraw consent or are lost to FU. Participants will be followed for overall survival and first subsequent anti-cancer therapy at 3-month intervals (\pm 14 d) at least for 1 year after starting treatment or until the last participant in the study has completed the active safety FU visit, or consent withdrawal or death or lost to follow up is reached for the last patient, whichever comes last. Participants may be contacted at additional times throughout the course of the study in order to collect survival data to ensure that long-term FU data is current.

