4.4 End of Study Definition

The end of the study is defined as the date of the last visit of the last participant (LPLV) in the study.

LPLV of a participant is reached if he/she has completed the last scheduled procedure shown in the Schedule of Activities (this also includes phone contacts during long-term FU) unless the patient died or withdrew consent or is lost to FU.

If the trial is stopped but benefits are observed for patients, further treatment options may be discussed and agreed between the investigator, sponsor and the patients and continued treatment in a Roll Over Study (ROS) or with commercial supply will be offered.

The LPLV date may also be reached based on the last participant switching to a roll-over study or being switched to commercial drug supply with no cost to the participant.

Primary completion

The primary completion of the study is defined by the event when all participants have been assessed for response rate (as defined by RECIST 1.1 or RANO) after the last participant has been followed for approximately 10 months unless they have discontinued before due to progression or any other reason.

5. Study Population

Prospective approval of protocol deviations to recruitment and enrollment criteria, also known as protocol waivers or exemptions, is not permitted.

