9.4.3 Secondary Endpoint(s)

The secondary efficacy endpoints in this study are Duration of Response (DOR), Disease Control Rate (DCR), PFS, 6 month PFS, according to RECIST 1.1 or RANO and additionally OS and 1 year OS in the Stage 2.

DOR (for PR and CR) is defined as the time (in days) from the first documented objective response of PR or CR, whichever is noted earlier, to first documented objective disease progression or death (if death occurs before progression is documented). DOR will be defined for responders only, i.e. participants with a CR or PR. The actual dates the tumor scans were performed will be used for this calculation. DOR for participants who have not progressed or died at the time of analysis will be censored at the date of their last tumor evaluation.

PFS is defined as the time (in days) from start of study intervention to the date of first objectively documented PD or death from any cause (if no progression is documented). The actual date of tumor assessments will be used for this calculation. PFS for participants without PD or death at the time of analysis will be censored at the date of their last tumor evaluation. PFS for participants who have neither tumor assessments nor death after baseline will be censored at Day 1.

OS is defined as the time (in days) from start of study intervention to the date of death due to any cause. If a participant is not known to have died, then OS will be censored at the date of last known date participant alive. If a participant is lost to FU before any assessment after assignment to study intervention, this participant will be censored at Day 1.

Safety is also considered as secondary endpoint. For details please refers to Section 9.4.5.

The secondary efficacy endpoints will be based on investigator assessments. Analyses will be done on the Full Analysis Set per cohort.

For analyses of the secondary endpoints, proportion-based efficacy variables will be using frequency tables as well as 80% two-sided Clopper-Pearson confidence intervals. With regard to time to event data, these will be summarized descriptively using Kaplan Meier methodology and plots, as well as median estimates based on Greenwood's formula, including 80% two-sided confidence interval

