5.6.				
5.6.2	•			
5.6.3				
5.7	Other Analyses			
5.7.				
5.7.2				
5.8	Interim Analyses			
5.8.				
6.	Supporting Documentation	8		
6.1	Appendix 1: List of Abbreviations			
6.2	Appendix 2: Changes to Protocol-planned Analyses			
6.3	Appendix 3: Baseline characteristics and demographics			
6.4	Appendix 4: Protocol deviations.			
6.5	Appendix 5: Medical history			
6.6	Appendix 6: Prior/concomitant/follow-up medications (including dictionary)			
7	Deferences	0		

Version 3.0 Page: 3 of 9

Version History

This statistical analysis plan (SAP) version 3.0 dated 12 MAR 2024 describes the analyses and data presentations for final clinical study report addendum when all participants have discontinued the trial. This SAP is based on the SAP version 2.0 dated 25 JAN 2023 and on 21136 integrated protocol amendment 1 dated 27 JAN 2021.

SAP Version	Date	Change	Rationale
1.0	08 JAN 2021	Not Applicable	Original version
2.0	25 JAN 2023	Not Applicable	Addendum to SAP 1.0 dated 08 JAN 2021 for primary completion analysis
3.0	12 MAR 2024	Adaptations for final analysis	

1. Introduction

Study 21136 is a multi-indication, single-treatment arm, open-label Phase 2 study of regorafenib in combination with nivolumab in patients with recurrent or metastatic solid tumors.

This study contains six cohorts:

- Head and Neck Squamous Cell Carcinoma (HNSCC) Immune Oncology (IO) naïve,
- Head and Neck Squamous Cell Carcinoma (HNSCC) Immune Oncology (IO) treated,
- Esophageal Squamous Cell Carcinoma (ESCC),
- Pancreatic ductal adenocarcinoma (PDAC),
- Biliary Tract Carcinoma (BTC),
- Glioblastoma Multiforme / Anaplastic Astrocytoma (GBM/AA).

The SAP describes the final analyses and data presentations at the time all participants had discontinued the trial.

Table, figure and listing specifications are contained in a separate document.

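### The SAP's 'duration of follow-up' is a plain summary of time to last contact or death, so it tracks survival rather than how long participants could be observed

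*SAP*

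**What the plan says.** SAP v3.0, Section 5.7.1, creates a follow-up variable for each cohort in support of the efficacy analyses. It is "the duration of follow-up defined as time from start of study-drug intake to last contact or death at the database cut-off date". The method is equally explicit: "Time will be summarized using descriptive statistics (number of observations, mean, standard deviation, minimum, median and maximum". Deaths and survivors are not separated, and the section does not refer back to SAP v2.0.

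Protocol 9.4.3 measures OS from start of study intervention to death from any cause. For survivors, "If a participant is not known to have died, then OS will be censored at the date of last known date participant alive". OS is analysed by Kaplan-Meier.

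On timing, Protocol 4.1.4 keeps participants in survival follow-up "at least for 1 year after starting treatment or until the last participant in the study has completed the active safety FU visit" (with further alternatives, the latest applying). Protocol 4.4 places primary completion "after the last participant has been followed for approximately 10 months". SAP v3.0 serves the "final clinical study report addendum when all participants have discontinued the trial". Neither document gives an accrual period or a data cut-off date.

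**The concern.** Length of follow-up is normally read as how long participants were, or could have been, under observation, and hence how mature the survival data are. The SAP quantity stops at death. A participant who dies at month 4 contributes 4 months of follow-up, although that outcome is completely known and no further observation was possible. In a cohort where most participants have died, the median is mainly a statement about when they died.

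The figure is printed separately for six cohorts whose prognosis differs. Under identical calendar follow-up, the cohort with worse survival would show the shorter duration. A reader judging OS maturity could take that as a shortfall in observation.

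**Working it through.** The plan states no follow-up figure, so there is none to reproduce. The check has an algebraic part and an illustration.

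**1. The bound.** Let T be time to death, C the time at which observation would otherwise end, and X = min(T, C). SAP 5.7.1 takes the ordinary median of X. Protocol 9.4.3 uses the same X with a death indicator, provided last contact equals last known alive. With no ties between deaths and censorings, the empirical curves satisfy

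S_X(t) = S_KM(t) × G_KM(t),

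where S_KM is the Kaplan-Meier curve for death and G_KM the one for censoring. As G_KM(t) ≤ 1, S_X(t) ≤ S_KM(t), so the plain median of X is at or below the Kaplan-Meier median OS. They agree when nobody is censored before that point.

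At odd n the result is exact. At even n it depends on how a median is taken when the curve sits at exactly 0.5. With the midpoint convention, the plain median exceeded the Kaplan-Meier median in at most 1.6% of simulated cohorts (n = 14), and only at even n. If the Kaplan-Meier median is instead the first time the curve is at or below 0.5, the plain median can exceed it by half the gap between the two middle observations.

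**2. Illustrative inputs.**
- Median OS (m), from other trials cited in Protocol 2.2. HNSCC: "The median OS for the nivolumab group was 7.5 months". ESCC: "median OS 10.9 months vs 8.4 months", of which the nivolumab figure is used. BTC: 5.4 months, 31.8 weeks (about 7.3 months) and 14.2 months. No numeric median OS is given there for PDAC or GBM/AA, so neither is computed.
- Assumed, not in the documents: exponential survival, no early loss, and time from first dose to cut-off uniform on (a, b) = 12–18, 12–36 or 24–36 months. Median potential follow-up is (a + b)/2 = 15, 24 or 30 months.

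**3. Formula.** The SAP median t solves 2^(−t/m) × G(t) = 0.5, with G(t) = 1 for t ≤ a and (b − t)/(b − a) for a < t < b. If m ≤ a, then t = m. For m = 14.2:
- 12–18 months: 2^(−12.5/14.2) × (18 − 12.5)/6 = 0.543 × 0.917 = 0.498, so t is about 12.5.
- 12–36 months: 2^(−13.2/14.2) × (36 − 13.2)/24 = 0.525 × 0.950 = 0.499, so t is about 13.2.
- 24–36 months: m is below 24, so t = 14.2.

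**4. Results in months: SAP median, with the gap to median potential follow-up in brackets.**

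| Assumed median OS | 12–18 | 12–36 | 24–36 |
|---|---|---|---|
| 5.4 (BTC, low) | 5.4 (9.6) | 5.4 (18.6) | 5.4 (24.6) |
| 7.3 (BTC) | 7.3 (7.7) | 7.3 (16.7) | 7.3 (22.7) |
| 7.5 (HNSCC) | 7.5 (7.5) | 7.5 (16.5) | 7.5 (22.5) |
| 10.9 (ESCC) | 10.9 (4.1) | 10.9 (13.1) | 10.9 (19.1) |
| 14.2 (BTC, high) | 12.5 (2.5) | 13.2 (10.8) | 14.2 (15.8) |

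Simulation at the planned full sizes (30 for HNSCC IO-naïve and ESCC, 45 for BTC; 20,000 replicates) agrees to about 0.1 month. For the extreme gaps, the 5–95% ranges are 1.3 to 5.3 months around 2.5 and 22.1 to 26.8 around 24.6.

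**5. Early loss.** With 10% or 20% lost by month 12 (12–36 range, n = 30, median OS 7.5), the simulated SAP median falls to 6.9 or 6.3 months. It then sits below median OS and still does not describe observation time.

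**6. Which range is nearer?** SAP v2.0 and v3.0 are dated about 13.5 months apart. If those dates lie near the two data cut-offs, minimum potential follow-up is about 10 + 13.5 = 23.5 months, which points to the 24–36 column. This is a pointer only.

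**The case against.** SAP 5.7.1 states exactly what it computes and never calls it follow-up for OS. The primary endpoint is ORR, and time actually observed is a legitimate descriptor for it. Time to last contact or death is a recognisable convention. That stands, and it is why the summary should be kept and renamed rather than removed.

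A reader might infer that the median can never exceed median OS. The documents do not support this without conditions, because nothing says that last contact and last known alive are the same date. If last contact were the earlier, the bound would still hold. If it were the later, the bound could fail. The even-n caveat also applies.

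SAP v2.0 was not available and may hold another follow-up estimate, so it cannot be said that the plan has none. Section 5.7.1 is, however, self-contained and does not point to v2.0.

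Maturity is partly visible elsewhere: Kaplan-Meier OS (Protocol 9.4.3, SAP 5.4.1.2), deaths (SAP 5.6.2), disposition (SAP 5.2) and swimmer plots (SAP 5.3.2). These help, but none corrects the label.

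Reverse Kaplan-Meier is also a weak sole remedy here. Under 24–36 months its median was not estimable in 55% of replicates at n = 9 with OS 7.5, 67% at n = 17 with OS 5.4, and 37–38% at n = 45 with OS 5.4. That objection is sound, so time to cut-off should be given for every cohort.

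**Conclusion.** The point holds as a matter of description and labelling, at minor severity. If last contact is the date last known alive, the SAP figure is OS time without its event indicator, and its median is governed by survival.

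The gap of about 2.5 to 25 months might be read as the size of a reporting error. It is not. It is the distance between two differently defined quantities, and it rests on historical single-agent survival, an exponential form and assumed cut-off ranges. In these settings the direction is firm and the size is not.

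Nor does the point reach the efficacy results. The ORR estimates, the exact tests and the Kaplan-Meier estimates are untouched, and no between-cohort comparison of follow-up is planned.

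**What to change.** In SAP 5.7.1:

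1. Rename the existing summary *time on study (to death or last contact)*, and state whether last contact is the last-known-alive date used for OS.
2. For every cohort, report first dose to database cut-off (median, minimum, maximum), with the numbers dead and censored before cut-off, or a cross-reference if the OS table already shows them.
3. Also report the reverse Kaplan-Meier median follow-up for OS (deaths censored, censoring as the event), printing *not estimable* where it applies.

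The cost is one or two more descriptive lines per cohort, from dates already needed for OS and the cut-off. Reverse Kaplan-Meier will often be imprecise or not estimable in small, short-survival cohorts. Time to cut-off counts time after withdrawal or loss, so it must be read beside the censored count.

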5.7.2 Subgroup Analyses

Subgroup analyses will not be performed.

5.8 Interim Analyses

Refer to main SAP v2.0, dated 25 JAN 2023.

5.8.1 Data Monitoring Committee or Other Review Board

Not applicable

Version 3.0 Page: 8 of 9

6. Supporting Documentation

6.1 Appendix 1: List of Abbreviations

Abbreviation	Definition	
AA	Anaplastic astrocytoma	
AE	Adverse event	
BTC	Biliary tract carcinoma	
CI	Confidence interval	
CR	Complete response	
DCR	Disease control rate	
DOR	Duration of response	
ESCC	Esophageal squamous cell carcinoma	
FAS	Full analysis set	
GBM	Glioblastoma multiforme	
HNSCC	Head and Neck Squamous Cell Carcinoma	
IMAE	Immune-mediated adverse event	
ORR	Overall response rate	
OS	Overall survival	
PD	Progression disease	
PDAC	Pancreatic ductal adenocarcinoma	
PFS	Progression free survival	
PR	Partial response	
RANO	Response assessment in neuro-oncology	
RECIST	Response evaluation criteria in solid tumors	
SAF	Safety analysis set	
SAP	Statistical analysis plan	
SD	Stable disease	

6.2 Appendix 2: Changes to Protocol-planned Analyses

Not applicable.

6.3 Appendix 3: Baseline characteristics and demographics

Baseline characteristics and demographics will not be presented in this report.

6.4 Appendix 4: Protocol deviations

Refer to main SAP v2.0, dated 25 JAN 2023

6.5 Appendix 5: Medical history

Medical history will not be presented in this report.

6.6 Appendix 6: Prior/concomitant/follow-up medications (including dictionary)

Medications will be summarized on the FAS population per cohort per main SAP v2.0, dated 25 JAN 2023.

CONFIDENTIAL	Statistical Analysis Plan
	BAY 73-4506 / 21136

Version 3.0 Page: 9 of 9

7. References

Not applicable.
